### 16.3 Data & Safety Monitoring

#### 16.31 Safety review

The principal investigator(s) and the study statistician will review the study monthly to identify accrual, adverse event, and any endpoint problems that might be developing. The Mayo Clinic Cancer Center (MCCC) Data Safety Monitoring Board (DSMB) is responsible for reviewing accrual and safety data for this trial at least biannually, based on reports provided by the MCCC Statistical Office.

#### 16.32 Adverse Event Stopping Rules

##### 16.321 Neoadjuvant

Enrollment will be temporarily halted during the neoadjuvant period if 2 or more of the first 6 patients enrolled or 30% or more thereafter develop any Grade 4 adverse event except cytopenias (anemia, thrombocytopenia, leukopenia, neutropenia); if the adverse event is possibly, probably, or definitely related to study treatment. All adverse event data will be reviewed by the study team and if appropriate, a protocol amendment will be drafted for IRB approval.

Enrollment to either study arm will be permanently halted if 2 or more out of first 6 patients or more than 30% of patients enrolled thereafter to that arm progress on therapy and as a result, their disease becomes unresectable.

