### Schema for Arms A and B

NOTE: Arms A and B are permanently closed to enrollment with MCCC Amendment 4

\*Cycle neoadjuvant = 28 days  $\pm$  3 days (maximum of 3 cycles of treatment)

Cycle surgery = ~4-6 weeks

\*\*Cycle adjuvant = 21 days  $\pm$  3 days (maximum of 8 cycles of treatment)

Total of 30 patients with 15 patients in each arm

[figure not shown]
Patients who do not have surgery will proceed to Survival Follow-up

If patient has disease progression confirmed by imaging during neo-adjuvant treatment that no longer deems them a surgical candidate, the patient proceeds to survival follow-up.

Generic name: Atezolizumab Brand name(s): Tecentriq® Mayo Abbreviation: ATEZO Availability: Genentech	Generic name: Cobimetinib Brand name(s): Cotellic® Mayo Abbreviation: COBI Availability: Genentech	Generic name: Vemurafenib Brand name(s): Zelboraf® Mayo Abbreviation: VEM Availability: Genentech
--	---	--

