### 1.9c2 Study Design

Arms A and B of MC1776 will continue accrual without change. Following completion of accrual to Arms A and B, accrual to Arm C will open to both BRAF-mutated and BRAF-wild-type patients.

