##### 16.322 Adjuvant

Enrollment will be temporarily halted during the adjuvant period if 2 or more of the first 6 patients receiving adjuvant treatment or 30% or more thereafter develop any Grade 4 adverse event except cytopenias (anemia, thrombocytopenia, leukopenia, neutropenia); if the adverse event is possibly, probably, or definitely related to study treatment. All adverse event data will be reviewed by the study team and if appropriate, a protocol amendment will be drafted for IRB approval.

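### The neoadjuvant Grade 4 halting rule in 16.321 names no arm, so as written its first-six trigger was used up before Arm C opened and its 30% trigger may be diluted by Arms A and B

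*Combined protocol and SAP*

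**What the plan says.** Section 16.321 holds two rules. The adverse event rule opens "Enrollment will be temporarily halted during the neoadjuvant period" and applies "if 2 or more of the first 6 patients enrolled or 30% or more thereafter develop any Grade 4 adverse event except cytopenias", provided the event is at least possibly related to study treatment. It names no arm. A halt leads to review by the study team and, if appropriate, an amendment.

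The second rule, on progression to unresectable disease, does name the arm. Its early part reads "Enrollment to either study arm will be permanently halted if 2 or more out of first 6 patients". Its later part is triggered when "more than 30% of patients enrolled thereafter to that arm progress on therapy". The word for a choice between two arms is still there, although the trial now has three.

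Section 16.322 repeats the Grade 4 rule for the adjuvant phase, "if 2 or more of the first 6 patients receiving adjuvant treatment or 30% or more thereafter", again without an arm.

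On the order of accrual, the schema for Arms A and B gives a planned 30 patients, 15 per arm, and states: "NOTE: Arms A and B are permanently closed to enrollment with MCCC Amendment 4". Section 1.9c2 says: "Following completion of accrual to Arms A and B, accrual to Arm C will open to both BRAF-mutated and BRAF-wild-type patients". Section 16.1112 plans 32 patients starting neoadjuvant treatment in Arm C, and 16.132 allows up to 36 enrolled. Section 16.1112 makes the evaluation of Arm C the same as that of Arms A and B for the primary objectives. It does not mention the halting rules.

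**The concern.** A two-in-six trigger is meant to catch a badly tolerated regimen early. If the six are the first six patients in the trial, that check took place in Arms A and B, on regimens containing cobimetinib with or without vemurafenib. Arm C gives atezolizumab with tiragolumab, and Appendix III itself says that clinical evaluation of tiragolumab is limited and that not all its risks are known.

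What remains for Arm C is the 30% trigger, and its denominator is not stated. If it carries Arm A/B patients, a high event rate in Arm C is averaged with up to 30 patients on other drugs. Two people applying the section to the same data could then disagree on whether enrollment must pause.

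**Working it through.** The plan gives no target rate and no halting probability for this rule, so there is no stated figure to reproduce.

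**Inputs from the documents.** Triggers of 2 in 6 and 30% (16.321); 30 planned patients in Arms A and B (schema); 32 patients in Arm C (16.1112); Arm C accrues after A and B (1.9c1, 1.9c2).

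**Assumptions.** Arms A and B reached their planned 30. They had e = 0, 3 or 6 qualifying events. The true rate p in Arm C is varied, with 30% as the main case. The documents give none of these.

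**Readings compared**, with x events among the first n Arm C patients and a check after each patient:

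1. Per arm: halt if x ≥ 2 with n ≤ 6, or x/n ≥ 0.30 with n ≥ 7.
2. 30% trigger on Arm C patients only, no first-six look: halt if x/n ≥ 0.30, checked from n = 7.
3. Pooled, all Arm A/B patients kept: halt if (e + x)/(30 + n) ≥ 0.30.
4. Pooled, the trial's first six left out because the trigger applies to those who follow: halt if (e + x)/(24 + n) ≥ 0.30, with e counted among those 24.

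**First six patients, per arm.** P(x ≥ 2) = 1 − (1 − p)^6 − 6p(1 − p)^5. At p = 0.30 this is 1 − 0.1176 − 0.3025 = 0.580. At p = 0.10 it is 0.114.

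**The same two events under pooling.** With e = 3 and two events in Arm C's first six, the pooled rate is (3 + 2)/(30 + 6) = 13.9%, so there is no halt. With e = 0 it is 2/36 = 5.6%; with e = 6 it is 8/36 = 22.2%. The earliest possible halt needs an unbroken run of Arm C events: 13, 9 or 5 in a row for e = 0, 3 or 6 with denominator 30 + n, and 11, 6 or 2 with 24 + n. At n = 32 and e = 3, reading 3 needs 0.30 × 62 = 18.6, so 19 events in total and 16 of 32 in Arm C. Reading 4 needs 0.30 × 56 = 16.8, so 17 in total and 14 of 32.

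**Chance of a halt, by exact binomial recursion:**

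| Reading | Prior A/B events | First 6, p = 30% | By 32, p = 30% | By 32, p = 40% |
|---|---|---|---|---|
| 1. Per arm | not used | 58% | 83% | 97% |
| 2. Arm C only, from 7th patient | not used | no check | 79% | 97% |
| 3. Pooled, 30 + n | 0 | 0% | 0.1% | 3% |
| | 3 | 0% | 2% | 21% |
| | 6 | 1% | 23% | 65% |
| 4. Pooled, 24 + n | 0 | 0% | 1% | 11% |
| | 3 | 0.1% | 10% | 46% |
| | 6 | 28% | 59% | 90% |

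Under reading 1, the chance of a halt by patient 32 is 14% at a true rate of 10% and 49% at 20%.

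**The case against.** The text never says that the count runs across the whole trial, and it does not say whether it restarts for Arm C. The leftover two-arm wording suggests that the section predates Arm C and was simply not revised, so a deliberate pooled rule cannot be read into it. That stands, and it is why the point is about an unstated counting unit.

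A reader might infer that Arm C has no working early safety stop, or that frequent Grade 4 events could never trigger a halt. The documents do not support either. The 30% trigger remains. On Arm C patients only, it halts with 79% probability at a true 30% rate, close to the per-arm 83%. Even pooled over 30 + n with 3 prior events, it halts with 62% probability by patient 32 if the true rate is 50%. What is lost on the literal reading is the first-six look; what may be weakened is the later trigger.

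Other oversight covers Arm C: monthly review by the principal investigators and statistician and DSMB review at least twice a year (16.31), rapid reporting of serious events (10.41), and a list of events of special interest for these two drugs (10.561). These matter, but none sets a numerical boundary for pausing enrollment. At the one patient per month expected in 16.132, about six Arm C patients could enroll between DSMB reviews six months apart.

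It is also tempting to extend the point unchanged to 16.322. That goes too far. Section 7.3 gives the same adjuvant atezolizumab in all arms, so pooling there is defensible; only the preceding neoadjuvant treatment differs.

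**Conclusion.** The concern holds as a defect of specification in 16.321. The rule names no arm, its neighbor does, and the section was not updated for a third arm. As written, the first-six trigger was used up before any patient received tiragolumab, and the 30% trigger is diluted if Arm A/B patients stay in its denominator.

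At a true 30% rate, the chance of a halt within 32 Arm C patients runs from 0.1% to 83% depending on the reading and on the prior event count. This spread rests on assumed true rates, assumed Arm A/B event counts and Arm A/B accrual at its planned 30. The low end belongs to the pooled reading with no prior events. If the 30% trigger covers Arm C patients only, the loss over 32 patients is small (79% against 83%), and the missing first-six look is the whole defect. For 16.322 the point is only that the counting unit is unstated.

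**What to change.** Keep the existing thresholds. In 16.321, state that both Grade 4 triggers are counted within each arm, that Arm C's count begins with its own first patient, and what the denominator of the later 30% trigger is. If the denominator is to be all patients so far in that arm, including its first six (the per-arm calculation above), say so explicitly, because the present wording does not settle it. In the progression rule, replace *either* with *any*, so that it plainly covers three arms. In 16.322, state whether the count is pooled or per arm; either can be defended.

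This takes about one sentence per rule in an amendment. The statistical cost of per-arm counting is some false temporary pauses: about a 14% chance over 32 patients if the true rate is 10%, of which 11.4 percentage points arise in the first six.

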**Expedited 24-hour notification followed by complete report within 3 calendar days for:**

- All Grade 4, and Grade 5 AEs

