### 10.62 Other routine reporting

Submit via appropriate MCCC Case Report Forms (i.e., paper or electronic, as applicable) the following AEs experienced by a patient and not specified in Section 10.6:

- 10.621 Grade 2 AEs deemed *possibly, probably, or definitely* related to the study treatment or procedure.
- 10.622 Grade 3 and 4 AEs regardless of attribution to the study treatment or procedure.
- 10.623 Grade 5 AEs (Deaths)
- 10.6231 Any death within 30 days of the patient's last study treatment or procedure regardless of attribution to the study treatment or procedure.
- 10.6232 Any death more than 30 days after the patient's last study treatment or procedure that is felt to be at least possibly treatment related must also be submitted as a Grade 5 AE, with a CTCAE type and attribution assigned.

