**Adverse Event Severity Grading Scale for Events Not Specifically Listed in NCI CTCAE**

Grade	Severity
1	Mild; asymptomatic or mild symptoms; clinical or diagnostic observations only; or intervention not indicated
2	Moderate; minimal, local, or non-invasive intervention indicated; or limiting age-appropriate instrumental activities of daily living a
3	Severe or medically significant, but not immediately life-threatening; hospitalization or prolongation of hospitalization indicated; disabling; or limiting self-care activities of daily living b,c
4	Life-threatening consequences or urgent intervention indicated d
5	Death related to adverse event d

NCI CTCAE = National Cancer Institute Common Terminology Criteria for Adverse Events.

Note: Based on the most recent version of NCI CTCAE (v5.0), which can be found at:

- a. Instrumental activities of daily living refer to preparing meals, shopping for groceries or clothes, using the telephone, managing money, etc.
- b. Examples of self-care activities of daily living include bathing, dressing and undressing, feeding oneself, using the toilet, and taking medications, as performed by patients who are not bedridden.
- c. If an event is assessed as a "significant medical event," it must be reported as a serious adverse event
- d. Grade 4 and 5 events must be reported as serious adverse events

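### The two adverse-event halting rules count Grade 4 events only, so a treatment-related death (Grade 5) does not itself count toward either threshold

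*Combined protocol and SAP*

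**What the plan says.** Section 16.32 contains two adverse-event halting rules.

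- Neoadjuvant (16.321): enrollment is halted temporarily if "2 or more of the first 6 patients enrolled or 30% or more thereafter develop any Grade 4 adverse event". With its exception, the event definition is that patients "develop any Grade 4 adverse event except cytopenias (anemia, thrombocytopenia, leukopenia, neutropenia"), and an event counts only "if the adverse event is possibly, probably, or definitely related to study treatment".
- Adjuvant (16.322): the same structure, triggered if "2 or more of the first 6 patients receiving adjuvant treatment or 30% or more thereafter develop any Grade 4 adverse event", with the same exception and attribution condition.

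In both cases the study team then reviews the adverse event data and, if appropriate, drafts an amendment.

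Section 16.321 also has a permanent, arm-level halt. It counts patients who "progress on therapy and as a result, their disease becomes unresectable", and so does not count toxicity or death.

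Deaths are handled in Section 10. Section 10.62 lists "Grade 5 AEs (Deaths") as an item of its own, apart from the item for Grades 3 and 4. The fallback severity scale in 10.83(e) defines Grade 4 as life-threatening and Grade 5 as death, and its footnote reads "Grade 4 and 5 events must be reported as serious adverse events". For late serious events, footnote 1 to 10.41 requires 24-hour notification of "All Grade 4, and Grade 5 AEs".

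**The concern.** A halting rule for toxicity should respond at least as readily to a fatal event as to a life-threatening one. As worded, these rules do not. Someone applying them literally would record a related death as Grade 5, find that the rule asks for Grade 4, and not count it.

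A pre-specified pause exists so that the decision to stop and look does not depend on judgement at the time. Here the most severe outcome is left to judgement and the less severe one is not. The setting adds weight: patients must have surgically resectable disease (3.33), and for Arm C, the only arm still enrolling, Appendix III says that clinical evaluation of tiragolumab is limited and that not all of its risks are known.

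**Working it through.** The plan states no error rate or operating characteristic for these rules, so there is no figure to reproduce. The main check is textual.

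**1. Does Grade 4 in the rules include Grade 5?** The provisions compare as follows.

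| Place | Grades named |
|---|---|
| 16.321 and 16.322, halting rules | 4 |
| 10.41, expedited timeframes | 3-5 |
| 10.41 footnote 1, late 24-hour reports | 4 and 5 |
| 10.62, routine reporting | 3 and 4 in one item, 5 in another |
| 10.83(e), footnote to the severity scale | 4 and 5 |
| Section 8 tables and 10.563 | open-ended forms such as ≥3 |

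The protocol uses explicit wording when it means more than one grade. Nothing in 16.32 extends Grade 4 upward.

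**2. Does another provision require a halt after a death?** Sections 10.52 and 10.62 require reporting. Section 10.84 requires notice to FDA within 7 calendar days, and a written report within 15, for the qualifying unexpected related events. Section 16.31 provides monthly review by the investigators and statistician, and DSMB review at least biannually. Appendix III mentions an iDMC. None of these attaches an enrollment halt to a death.

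**3. The count in the first 6 patients.** The threshold is 2.

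- Two related deaths, with no separately recorded related non-cytopenia Grade 4 event: the proportion is 2/6 = 33%, but the qualifying count is 0. No halt.
- Two related non-fatal, non-cytopenia Grade 4 events: the qualifying count is 2. Halt.
- On the same condition, 6 related deaths in 6 patients also give a qualifying count of 0.
- A patient with a recorded qualifying Grade 4 event who later dies counts as 1, through the Grade 4 event.

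The same applies to the 30% limb. If the percentage is taken over all patients in an arm, 30% means 5 of 15 (0.30 × 15 = 4.5, rounded up) or 10 of 32 (0.30 × 32 = 9.6, rounded up), again counting Grade 4 events only.

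**4. Illustration of size.** Let p be the chance that a patient has a counted event. The chance of at least 2 in 6 is

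P = 1 − (1 − p)^6 − 6p(1 − p)^5.

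As written, p is the related Grade 4 rate. With deaths counted, p is the sum of the related Grade 4 and Grade 5 rates. Each patient is classed by worst grade, so the deaths here carry no separately recorded Grade 4 event. The rates are assumptions and do not come from the documents.

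| Grade 4 rate | Grade 5 rate | P(halt in first 6), as written | P(halt in first 6), Grade 5 counted |
|---|---|---|---|
| 5% | 2% | 3.3% | 6.1% |
| 5% | 5% | 3.3% | 11.4% |
| 10% | 2% | 11.4% | 15.6% |
| 10% | 5% | 11.4% | 22.4% |
| 10% | 10% | 11.4% | 34.5% |

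Example for the second row: as written, 1 − 0.95^6 − 6(0.05)(0.95^5) = 1 − 0.7351 − 0.2321 = 0.0328. With p = 0.10, 1 − 0.5314 − 0.3543 = 0.1143.

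**The case against.** The strongest reply is that a fatal event would not go unnoticed. Any death within 30 days of the last dose, and any later death at least possibly related, must be reported within 24 hours (10.52). Unexpected related fatal events go to FDA within 7 calendar days (10.84), and unanticipated problems have a route to the IRB (10.51). The investigators and statistician review adverse events monthly, and the DSMB interval in 16.31 is a minimum frequency. The sponsor is primarily responsible for the study's benefit-risk balance (10.85). All of this stands. A reader might infer that deaths could accumulate unseen between DSMB meetings while accrual continues, but the documents do not support that. What they leave open is narrower: every one of these routes permits a halt and none requires it.

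Two other strong readings also fail. One is that a patient who dies can never contribute to a halt. That is wrong, because a qualifying Grade 4 event recorded before the death still counts. The other is that these are the only quantitative safety boundaries. The permanent halt for progression to unresectable disease is also quantitative and guards against a real harm of delaying surgery; it simply does not count deaths.

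It can also be said that the authors plainly meant Grade 4 or higher. That is likely, but it is an argument for writing it down.

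**Conclusion.** The gap is real and is the same in both rules. A related Grade 5 event does not itself count toward the 2-of-6 or 30% thresholds, and no other provision makes a death halt enrollment. In the clearest case, two related deaths in the first 6 patients contribute 0 of the 2 events needed. That result rests on the literal wording and on there being no separately recorded qualifying Grade 4 event in those patients. The binomial figures depend on assumed rates and only show scale; the conclusion does not need them.

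The gap affects no endpoint, sample size or estimate. It is most probably a drafting omission, but it sits in the only written adverse-event boundaries.

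A reader might go further and infer that the plan must halt after any single related death. The documents give no basis for that. The existing rule needs two events in the first six, and would still need two with Grade 5 counted. Whether one related death should prompt a formal review is a separate choice for the sponsor.

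**What to change.** In 16.321 and 16.322, change the counted event from Grade 4 to Grade 4 or 5. Limit the cytopenia exception to non-fatal events; otherwise a death recorded under one of the excepted terms would still be left out. Keep the attribution condition and both thresholds unchanged.

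The cost is a few words in a protocol amendment. Enrollment may pause somewhat more often, because patients with a related fatal event would then count. The pause remains temporary and leads to the same study-team review already described.

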##### 16.322 Adjuvant

Enrollment will be temporarily halted during the adjuvant period if 2 or more of the first 6 patients receiving adjuvant treatment or 30% or more thereafter develop any Grade 4 adverse event except cytopenias (anemia, thrombocytopenia, leukopenia, neutropenia); if the adverse event is possibly, probably, or definitely related to study treatment. All adverse event data will be reviewed by the study team and if appropriate, a protocol amendment will be drafted for IRB approval.

### 16.4 Subset Analyses for Minorities

#### 16.41 Study availability

This study will be available to all eligible patients, regardless of gender, race or ethnic origin.

#### 16.42 Statistical analysis by subset

There is no information currently available regarding differential effects of this regimen in subsets defined by race, gender, or ethnicity, and there is no reason to expect such differences to exist. Therefore, although the planned analyses will look for differences in treatment effect based on racial groupings, the sample size is not increased in order to provide additional power for subset analyses.

## 16.43 Regional population

The geographical region served by MCCC has a population which includes approximately 3% minorities. Expected sizes of racial by gender subsets are shown in the following table:

Accrual Targets			
Ethnic Category	Sex/Gender		
	Females	Males	Total
Hispanic or Latino	0	3	3
Not Hispanic or Latino	27	36	63
Ethnic Category: Total of all subjects	27	39	66
Racial Category			
American Indian or Alaskan Native	0	0	0
Asian	0	0	0
Black or African American	0	0	0
Native Hawaiian or other Pacific Islander	0	0	0
White	27	39	66
Racial Category: Total of all subjects	27	39	66

**Ethnic Categories:** **Hispanic or Latino** – a person of Cuban, Mexican, Puerto Rican, South or Central American, or other Spanish culture or origin, regardless of race. The term “Spanish origin” can also be used in addition to “Hispanic or Latino.”

**Not Hispanic or Latino**

**Racial Categories:** **American Indian or Alaskan Native** – a person having origins in any of the original peoples of North, Central, or South America, and who maintains tribal affiliations or community attachment.

**Asian** – a person having origins in any of the original peoples of the Far East, Southeast Asia, or the Indian subcontinent including, for example, Cambodia, China, India, Japan, Korea, Malaysia, Pakistan, the Philippine Islands, Thailand, and Vietnam. (Note: Individuals from the Philippine Islands have been recorded as Pacific Islanders in previous data collection strategies.)

**Black or African American** – a person having origins in any of the black racial groups of Africa.

**Native Hawaiian or other Pacific Islander** – a person having origins in any of the original peoples of Hawaii, Guam, Samoa, or other Pacific Islands.

**White** – a person having origins in any of the original peoples of Europe, the Middle East, or North Africa.

